## Subject Recruitment and Compensation

- Describe recruitment procedures, including who will introduce the study to potential subjects. Describe how you will ensure that subject selection is equitable and all relevant demographic groups have access to study participation (per 45 CFR 46.111(a) (3)). Include information about approximately how many DUHS subjects will be recruited. If subjects are to be compensated, provide specific prorated amounts to be provided for expenses such as travel and/or lost wages, and/or for inducement to participate.

Aim 1: Study participants will be recruited during community screening events organized and hosted by El Centro Hispano as part of their community health outreach services. We anticipate ~150 participants to be recruited from 3-4 screening events scheduled during the course of the study. El Centro Hispano's clinical staff will introduce the study to event attendees and those interested in participating or learning more about the study will be "handed off" to the study team who will review the informed consent with each person individually and confidentially, allowing them to ask questions before deciding whether to consent or not.

Aim 2: PCPs at DOC who care for racial and ethnic minorities with T2D will be recruited to participate in the provider-facing intervention. Since the intervention follows the "standard of care," we will not consent PCPs.

Participants in Aim 1 of the study will be compensated with a gift valued at no more than \$10.

### Consent Process

- Complete the consent section in the iRIS Submission Form.

### Subject's Capacity to Give Legally Effective Consent

- If subjects who do not have the capacity to give legally effective consent are included, describe how diminished capacity will be assessed. Will a periodic reassessment occur? If so, when? Will the subject be consented if the decisional capacity improves?

Aim 1: Only subjects attending community screening events who have the capacity to give consent will be eligible to participate in this study.

Aim 2: PCPs are provided recommendations that follow the standard of care. No consents are necessary since there is no contact between the study team and patients and PCPs can choose whether or not to follow the recommendations

### Study Interventions

- If not already presented in #4 above, describe study-related treatment or use of an investigational drug or biologic (with dosages), or device, or use of another form of intervention (i.e., either physical procedures or manipulation of the subject or the subject's environment) for research purposes.

See #4:

### Risk/Benefit Assessment

- Include a thorough description of how risks and discomforts will be minimized (per 45 CFR 46.111(a) (1 and 2)). Consider physical, psychological, legal, economic and social risks as applicable. If vulnerable populations are to be included (such as children, pregnant individuals, imprisoned persons or cognitively impaired adults), what special precautions will be used to minimize risks to these subjects? Also identify what available alternatives the person has if he/she chooses not to participate in the study. Describe the possible benefits to the subject. What is the importance of the knowledge expected to result from the research?

UACR testing will be provided by the study as an additional screening tool to the standard of care tests being conducted. This test requires a urine sample collection that will be offered to all consenting participants. The potential loss of confidentiality may be a risk of this procedure and every effort will be made to protect confidentiality, as with all study patient data.

## Costs to the Subject

- Describe and justify any costs that the subject will incur as a result of participation; ordinarily, subjects should not be expected to pay for research without receiving direct benefit.

The study is only identifying patients who are eligible for an updated UACR, per standard of care guidelines and recommending that the PCP order the test at the patient's next clinic visit with them. The PCP will make the decision whether or not to order the updated UACR as part of standard of care practices for the patient's next visit.

## Data Analysis & Statistical Considerations

- Describe endpoints and power calculations. Provide a detailed description of how study data will be analyzed, including statistical methods used, and how ineligible subjects will be handled and which subjects will be included for analysis. Include planned sample size justification. Provide estimated time to target accrual and accrual rate. Describe interim analysis including plans to stop accrual during monitoring. Phase I studies, include dose escalation schema and criteria for dose escalation with definition of MTD and DLT.

### Aim 1:

Statistical Analysis: Descriptive statistics will be used to report the proportion of participants who successfully attended a PCP visit, have a pending PCP visit, or attempted to schedule a PCP visit, characterizing the screening population by sociodemographic data, known health status, lifestyle behaviors, and family history. Mean values and prevalence rates for all categorical variables will be examined using Fisher's exact test, with Independent Student's t-test used for all continuous variables.

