## Design & Procedures

- Describe the study, providing details regarding the study intervention (drug, device, physical procedures, manipulation of the subject or the subject's environment, etc.). Discuss justifications for placebo control, discontinuation or delay of standard therapies, and washout periods if applicable. Identify procedures, tests and interventions performed exclusively for research purposes or more frequently than standard of care. Include alternative therapies, concurrent therapies discontinued per protocol, risk benefit ratio, and use of tissue/specimens. Discuss monitoring during washout periods if applicable. Include brief description of follow-up, if any.

**Specific Aim 1:** Increase rates of CKD screening and monitoring for Hispanic/Latinx community members in Durham, NC.

In order to identify people with CKD (i.e. albuminuria) or CKD risk factors, such as T2D, hypertension, and /or elevated body mass index (BMI) we will utilize an existing NKF framework and a well-known, community-based Hispanic/Latinx outreach organization (El Centro Hispano) and the community screening events they conduct for Hispanic/Latinx individuals in the community.

**Data Source:** Hispanic/Latinx Individuals at El Centro Hispano-coordinated community health screening events

**Study Design & Participants:** Working with El Centro Hispano and NKF of North Carolina, we will build upon existing North Carolina (NC) screening frameworks to engage Hispanic/Latinx individuals in Durham, North Carolina. El Centro Hispano organizes patient-centered health-screening events for Hispanics/Latinx at different locations throughout the Durham community (e.g. churches, community centers, embassies). These events offer routine screening for blood pressure and BMI (and at times, hemoglobin A1Cs) performed by certified healthcare workers or nursing students. Study participants will be recruited from those attending the screening events so no further recruitment or recruitment materials are required. The study will be introduced to the attendees by El Centro clinical staff at the events. Those interested in participating or learning more about the study will be "handed off" to the study team go over the informed consent, answer any questions and conduct the consent process.

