In total, we plan to enroll ~150 Hispanic/Latinx participants from 3-4 community screening events organized and hosted by El Centro Hispano, who has also agreed to provide bilingual community health workers and equipment needed to perform hypertension and BMI screenings on Hispanic/Latinx individuals who come to the events, at no cost to the study team. Individuals who choose not to sign the informed consent will receive the BMI and BP screenings and information typically provided at these community events.

Consent will be obtained digitally via iPad and stored securely in RedCap. An electronic copy of the signed consent will be emailed to the participant.

For participants without an email address, a paper consent will be provided and a signed copy given to them for their records.

For screened participants who sign an informed consent form, El Centro Hispano will leverage their existing relationships with nursing students to perform point of care HbA1C tests in order to identify participants with diabetes or pre-diabetes. The study will supply the funds for these tests. An additional screening test will also be provided for consented participants to identify those with proteinuria (protein in the urine). This is done using a urine dipstick tests, which will be provided by NKF of NC as part of their kidney education awareness program.

The NKF of NC is a local NKF affiliate serving individuals in the state of NC and focused on increasing awareness about kidney health. Their programs have targeted groups who face higher risk of kidney disease, including Hispanics/Latinx. [name], primary mentor, has been Chair of the NKF of NC Medical Advisory Board since 2018. The NKF of NC has an established partnership with the University of North Carolina entitled the Kidney Education Outreach Program (KEOP), to screen patients for urinary signs of kidney damage.

All consented participants will be provided language-concordant information on kidney health, that have been created by the National Kidney Foundation (attached to this proposal) and are publicly available. For those with an abnormal result on a screening test, additional targeted materials will be provided (e.g.

blood pressure and kidney health) and will also be provided a recommendation to make an appointment with a PCP and options on how to do so (including with community-based health centers such as Lincoln Community Health Center (LCHC) and Duke Outpatient Clinic (DOC)).

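### Aim 1 is worded as raising CKD screening rates, but its single cohort has no reference rate, and the group tests planned for it name no groups

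*Combined protocol and SAP*

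**What the plan says.** Under Design & Procedures, Specific Aim 1 is to "Increase rates of CKD screening and monitoring for Hispanic/Latinx community members in Durham, NC". The Purpose of the Study section words it in much the same way.

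The participants form one group. "Study participants will be recruited from those attending the screening events", and "In total, we plan to enroll ~150 Hispanic/Latinx participants from 3-4 community screening events organized and hosted by El Centro Hispano". Blood pressure and BMI are routine at these events, and HbA1c is sometimes offered. For people who consent, the study adds a point-of-care HbA1c and a urine dipstick. Of those who decline, the protocol says "Individuals who choose not to sign the informed consent will receive the BMI and BP screenings"; it describes no data collection on them. It also says "For those with an abnormal result on a screening test, additional targeted materials will be provided", and these same people are advised to see a primary care provider (PCP).

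The Aim 1 paragraph of Data Analysis & Statistical Considerations has two parts. The first is descriptive: "Descriptive statistics will be used to report the proportion of participants who successfully attended a PCP visit", or who have one pending or tried to schedule one, with a description of the screened population that includes known health status. The second reads "Mean values and prevalence rates for all categorical variables will be examined using Fisher's exact test" and assigns the independent Student's t-test to all continuous variables. No groups, hypothesis or sample-size rationale are given.

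**The concern.** An increase is a difference between two rates, and each rate needs a denominator. Aim 1 supplies neither a rate before the events nor one from a comparable population. Within the cohort, being offered testing is a consequence of enrolment, so the proportion screened says nothing about change in the community.

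The two named tests have the same gap on a smaller scale. Each compares groups, and the plan applies them to every variable without saying which groups. The sentence also pairs mean values with categorical variables, which Fisher's exact test does not address.

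Two things are at stake. A report could present the number screened as evidence that screening rates rose. And the comparisons eventually published could be those chosen once the data were in. Meanwhile, what this design can deliver well, the yield of abnormal findings and the follow-through to primary care, has no stated precision and no explicit separation of new findings from conditions already known.

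**Working it through.** The plan states no power, significance level, effect size or derivation for the target of about 150, so there is no figure to reproduce. The check has two parts: a search for a comparator, and the precision that 150 people give.

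**1. Is there a reference for an increase?** Candidates in the documents:

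- *A baseline period.* The 3-month pre/post comparison under Design & Procedures and in the Aim 2 analysis is at PCP level and belongs to Aim 2 only.
- *An external rate.* Background & Significance cites a national figure of 21% for UACR testing in people with hypertension or type 2 diabetes. It is background, is not planned as a reference, and describes a different population.
- *Attendees who decline consent.* They receive routine BMI and blood pressure checks, but no comparison with them is planned.

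None supplies a reference rate or a community denominator.

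**2. Can the tests be run as written?** With no grouping variable, the table for Fisher's exact test has an empty column. For example, 60 and 90 in one column and zeros in the other give an undefined odds ratio and p = 1. The t-test has no second sample. With a grouping inside the cohort, both can be computed. Two natural groupings exist, abnormal versus normal screen and PCP visit attended versus not, but the analysis text assigns neither to the tests.

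**3. Precision for the whole cohort.** The 95% half-width is 1.96 × √(p(1−p)/n). At n = 150 and p = 0.5 this is 1.96 × √(0.25/150) = 0.080, the largest value. Exact (Clopper-Pearson) 95% intervals:

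| Observed | 95% interval |
|---|---|
| 15/150 (10%) | 5.7% to 16.0% |
| 45/150 (30%) | 22.8% to 38.0% |
| 75/150 (50%) | 41.7% to 58.3% |

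**4. Precision among abnormal screens.** Their number is not given. If it were 75, the largest half-width would be 1.96 × √(0.25/75) = 0.113. If it were 50, it would be 1.96 × √(0.25/50) = 0.139. Both counts are assumptions.

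**5. Clustering by event (assumption only).** Three to four events give 150/4 = 37.5 to 150/3 = 50 people each. The design effect is 1 + (m − 1) × ICC. The documents give no ICC. An assumed range of 0.01 to 0.05 gives 1 + 36.5 × 0.01 = 1.37 up to 1 + 49 × 0.05 = 3.45. Applied to the Wilson half-width at 75/150 (42.1% to 57.9%, or 7.9 points), this gives 7.9 × √1.365 = 9.2 up to 7.9 × √3.45 = 14.7 points.

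**6. What a within-cohort contrast could detect.** Assuming two-sided 5% significance, 80% power and the splits shown:

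| Split | Detectable difference from 30% or 50% | Continuous variable |
|---|---|---|
| 75/75 | about 22 points | 0.46 SD |
| 50/100 | about 24 points | 0.49 SD |
| 30/120 | 27 to 28 points | 0.57 SD |

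The SD column is (1.96 + 0.84) × √(1/n₁ + 1/n₂); for 75/75 this is 2.80 × √(2/75) = 0.46. The differences in points use the normal approximation. By enumeration, Fisher's exact test with 75/75 and true rates of 30% and 50% has power of about 67%.

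**The case against.** The best defence is that the aim's wording is a service goal. The study adds HbA1c and urine testing to events that otherwise offer less, and in that sense more people are screened. No section plans to estimate or test an increase for Aim 1, and the Purpose of the Study section anticipates identifying patients and establishing feasibility. The first sentence of the analysis is descriptive and suits a small pilot.

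Most of this stands, and it rules out several stronger readings. A reader might infer that Aim 1 cannot be carried out at all. It can: the screening, the PCP-visit proportions and the prevalence rates are all feasible in one cohort. A reader might infer that Fisher's exact test and the t-test are invalid here. They are under-specified, and would be sound for a named within-cohort contrast. A reader might infer that the plan commits to concluding that rates rose. It does not; the claim lies in the wording of the aim. Nor is screening yield left without any estimator, since prevalence rates are named. What is missing is the list of results to be reported and their intervals. Known health status is also to be collected, so only the explicit known-versus-new split is absent.

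What the defence does not supply is a reference rate or the groups for the tests. If Aim 1 is purely descriptive, the plan should say so, and the test sentence should be defined or removed.

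**Conclusion.** The concern holds in a limited form. Aim 1 as designed cannot show an increase in screening rates, and its two group tests cannot be run without choosing contrasts that the plan does not name. Both conclusions follow from the text and need no assumption.

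The numbers describe what the design can deliver. A proportion of the whole cohort would be known to within about 8 points at worst, if about 150 are enrolled and clustering by event is ignored. Estimates among abnormal screens would be less precise, by an amount that depends on a count the documents do not give. The wider figures that allow for clustering rest entirely on an assumed ICC and should not be read as a finding about this study. The number of variables to be tested is not stated, so no false-positive rate is put on the unnamed tests. Nothing here affects the Aim 2 comparison.

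**What to change.** - Restate Aim 1, in Purpose of the Study and in Design & Procedures, as estimating the yield of screening and linkage to PCP care. To keep a claim of increase, the plan would need to add a reference rate with its denominator.
- In the Aim 1 analysis, replace the Fisher and t-test sentence with a proportion (or mean) and 95% confidence interval for each screening result: blood pressure, BMI, HbA1c and urine protein.
- Split these into previously known and newly identified, using the planned data on known health status where they are recorded by condition.
- Report PCP linkage among participants with an abnormal screen, since they are the ones advised to see a PCP, and state that denominator.
- If a group test is kept, prespecify one contrast, for example PCP visit attended versus not attended among abnormal screens, and label it exploratory.

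The cost is mainly wording in three sections and a more modest Aim 1 claim. The known-versus-new split needs history recorded condition by condition. The documents do not show whether that is planned, so the data collection form should be checked.

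### Aim 1 names the pooled-variance Student's t-test for groups it does not define; Welch's test is a safer default at almost no cost, and results should also be shown by event

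*Combined protocol and SAP*

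**What the plan says.** The Aim 1 part of Data Analysis & Statistical Considerations opens with description: "Descriptive statistics will be used to report the proportion of participants who successfully attended a PCP visit", together with those who "have a pending PCP visit, or attempted to schedule a PCP visit". It then names two tests. For categorical data, "Mean values and prevalence rates for all categorical variables will be examined using Fisher's exact test"; the sentence continues "with Independent Student's t-test used for all continuous variables". It does not say which groups the tests compare, and gives no group sizes, hypothesis, significance level or confidence interval.

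On where the sample comes from, Design & Procedures states "we plan to enroll ~150 Hispanic/Latinx participants from 3-4 community screening events", and Subject Recruitment and Compensation agrees: "We anticipate ~150 participants to be recruited from 3-4 screening events". The events are held "at different locations throughout the Durham community (e.g. churches, community centers, embassies"). Neither named test uses the event, and no reporting by event is planned.

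**The concern.** Two features of the planned analysis sit poorly with the sample it will meet.

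First, Student's test rests on a common variance. Screening subgroups, such as abnormal against normal result or attended against not attended, need not be of similar size or spread. When both differ, the pooled standard error is wrong. An apparent difference may then be spurious, or a real one may be missed. Because the groups are not named, nobody can say beforehand which way the error would run.

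Second, both tests, and any simple binomial limits, treat about 150 people as independent, although they are recruited in 3-4 batches at different venues. If people at one event resemble each other, overall proportions are less precise than 150 independent observations would suggest. Proportions are the main Aim 1 output.

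**Working it through.** The plan gives no power calculation, interval or p-value for Aim 1, so there is no figure of its own to reproduce.

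**Inputs from the documents.** About 150 participants; 3-4 events, so 150/4 = 37.5 to 150/3 = 50 people per event; Student's t-test and Fisher's exact test.

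**Assumed inputs.** Two-sided 5% level; group splits from 110/40 to 135/15; SD ratios 1.5 and 2; prevalence 30%; event intraclass correlation (ICC) 0.01, 0.02 and 0.05. The documents give none of these.

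**Step 1: unequal variances.** The true variance of the difference in means is s1²/n1 + s2²/n2. Student's test estimates it by [((n1−1)s1² + (n2−1)s2²)/148] × (1/n1 + 1/n2). By hand for 110/40:

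- SD 1 in the larger group, 1.5 in the smaller. True: 1/110 + 2.25/40 = 0.0653. Pooled: (109 + 39 × 2.25)/148 × 0.03409 = 0.0453. Ratio 1.44. The effective cut-off falls from 1.976 to 1.976/√1.44 = 1.65, a type I error of about 10%.
- SDs exchanged. True: 2.25/110 + 1/40 = 0.0455. Pooled: (109 × 2.25 + 39)/148 × 0.03409 = 0.0655. Ratio 0.69. The cut-off rises to about 2.37, a type I error of about 1.8%.

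Simulation with equal-mean normal data, 40,000 runs per row:

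| Larger/smaller group | SDs (larger, smaller) | True ÷ pooled variance | Student | Welch |
|---|---|---|---|---|
| 110/40 | 1, 1.5 | 1.44 | 10.2% | 5.1% |
| 110/40 | 1, 2 | 1.79 | 14.7% | 5.1% |
| 120/30 | 1, 1.5 | 1.61 | 11.8% | 4.9% |
| 120/30 | 1, 2 | 2.14 | 18.2% | 5.1% |
| 130/20 | 1, 1.5 | 1.80 | 14.1% | 5.1% |
| 130/20 | 1, 2 | 2.60 | 22.5% | 5.0% |
| 135/15 | 1, 1.5 | 1.90 | 15.5% | 5.0% |
| 135/15 | 1, 2 | 2.88 | 24.8% | 5.0% |
| 110/40 | 1.5, 1 | 0.69 | 1.9% | 4.8% |
| 110/40 | 2, 1 | 0.56 | 0.9% | 4.9% |
| 120/30 | 1.5, 1 | 0.62 | 1.4% | 5.1% |
| 120/30 | 2, 1 | 0.47 | 0.4% | 5.0% |
| 130/20 | 1.5, 1 | 0.56 | 0.9% | 5.0% |
| 130/20 | 2, 1 | 0.39 | 0.2% | 5.0% |

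With equal SDs, Student's test gives 4.9-5.2% at these splits. With 75/75 and unequal SDs it gives 4.9-5.1% (20,000 runs). The trouble needs unequal sizes and unequal variances together.

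**Step 2: overall proportions.** Design effect = 1 + (m − 1) × ICC, with m people per event. Half-width = 1.96 × √(0.3 × 0.7/150 × design effect). With no clustering this is 1.96 × √0.0014 = 7.3 points. Actual coverage of the uncorrected 95% interval is approximately 2Φ(1.96/√design effect) − 1.

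| ICC | Design effect, 4 events / 3 events | Half-width, points | Coverage of uncorrected interval |
|---|---|---|---|
| 0.01 | 1.365 / 1.49 | 8.6 / 9.0 | 91% / 89% |
| 0.02 | 1.73 / 1.98 | 9.6 / 10.3 | 86% / 84% |
| 0.05 | 2.825 / 3.45 | 12.3 / 13.6 | 76% / 71% |

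**Step 3: subgroup p-values under clustering.** The design effect above does not carry over to a contrast made within events. Simulated type I error of the ordinary t-test with 3-4 events (20,000 runs per case):

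- subgroup spread evenly over events: 4.0-5.1% for ICC 0.01-0.10;
- subgroup share running from 15% to 45% across events: 5.0-7.1% for ICC 0.01-0.05;
- share running from 5% to 60%: 6.0-11.9% for the same ICCs;
- groups that are the events themselves: 9.4-10.9% at ICC 0.01 and 24.1-29.9% at ICC 0.05.

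**Step 4: Fisher's test.** It makes no equal-variance assumption. With independent people its size is 2.7-4.2% for splits of 75/75, 110/40 and 120/30 and event rates of 10%, 30% and 50%.

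**The case against.** The strongest reply is that this matters little. Aim 1 is descriptive and drawn from people attending outreach events. It has no powered comparison, and nothing in the documents turns on an Aim 1 p-value. No interval is planned, so the half-widths in Step 2 concern limits that someone would have to add. The ICCs, SD ratios and splits are all assumed. This stands, and it sets the weight of the point.

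A reader might go further and infer that the Aim 1 tests will be systematically too optimistic. The documents do not support that:

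- The direction for Student's test is open. A smaller abnormal group with more variable values is plausible, but the events screen blood pressure, BMI, HbA1c and urine protein, so people abnormal on at least one test could be the majority. If they were also more variable, the test would be conservative. HbA1c is an awkward example in any case, because groups defined by it differ on it by construction.
- Unequal group sizes alone do no harm, as the equal-SD runs show.
- The equal-variance problem belongs to the t-test only. Fisher's test does not share it and is itself conservative with independent people.
- Clustering does not inflate a comparison spread evenly over events. Serious inflation needs a subgroup share that varies strongly by event, or a comparison of the events themselves, which the plan does not mention.

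The reply does not rescue Student's test as the default. With the groups undefined the sign of the error cannot be known beforehand, which is a reason to choose the test that holds its level either way.

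**Conclusion.** The point holds as a cheap improvement with minor consequence. Where group sizes and variances both differ, Student's test can have a type I error of about 10-25% (smaller group of 15-40 more variable) or about 0.2-2% (larger group of 110-130 more variable) against a nominal 5%; Welch's test held 4.8-5.2% in these settings. These figures assume normal data, a total of 150 and SD ratios of 1.5-2.

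The clustering part is conditional. Limits on overall proportions would be too narrow only if limits are reported and people within an event are alike; the size rests wholly on the assumed ICC. Subgroup p-values are affected mainly if subgroup share differs by event. The documents do not show that Aim 1's conclusions would be wrong, or wrong in a particular direction.

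**What to change.** In the Aim 1 statistical paragraph:

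1. Replace Student's t-test with Welch's t-test, and name the groups to be compared.
2. Show each main proportion by event beside the pooled figure. If limits are given for the pooled figure, say that they ignore variation between events.
3. As a supportive check, adjust subgroup comparisons for event: a stratified exact or Mantel-Haenszel test for categorical variables, and event as a fixed factor for continuous ones. Three or four events are too few for reliable cluster-robust or random-effect variances.
4. Label all Aim 1 p-values exploratory.

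The cost is wording, provided the event is recorded for each participant at enrolment. Sample size and procedures do not change. The downside is slightly less power when variances are in fact equal and groups are small, and any limits reported would carry an explicit caveat.
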